9. STATISTICAL METHODS

All statistical methods shall be detailed in a SAP that will be finalized prior to the database lock and unblinding. All relevant data collected in this clinical study will be documented using summary tables, figures, and subject data listings.

[figure not shown]
Any deviations from the CSP are to be justified in the SAP.

9.1. Determination of Sample Size

Up to 30 subjects are planned to be randomized 2:1, i.e. 20 subjects will receive GLPG3970 (400 mg q.d.) and 10 subjects will receive placebo. In case of drop-outs due to SARS-CoV-2 infection, additional subjects may be randomized on top of the planned sample size. The number of additional subjects randomized will not exceed the number of subjects dropping out of the study in relation to SARS-CoV-2. Randomization of additional subjects will be decided by the sponsor before study lock or related unblinding has occurred.

This sample size provides favorable operating characteristics for the primary efficacy endpoint (i.e. ESSDAI change from baseline at Week 12) in terms of the modified signal detection methodology (21). This methodology will be used to provide further insight into the treatment effect of GLPG3970 over placebo, and will support scenario analyses. The posterior distribution of this treatment effect will be estimated, and from this distribution probabilities of reaching at least a certain effect (delta) will be derived, e.g. a range of plausible effect size values going from as high as $P(\delta \leq -5)$ to as low as $P(\delta \leq -2)$. A common SD of 4 was assumed for both active and placebo arm.

Probability	Reference value	Outcome
0.852	-5	Signal detected
0.041		No conclusion
0.107		Signal not detected
0.427	-3	Signal detected
0.088		No conclusion
0.485		Signal not detected
0.205	-2	Signal detected
0.050		No conclusion
0.745		Signal not detected

9.2. Population for Analyses

9.2.1. All Screened Subjects

All subjects who signed and dated an ICF.

9.2.2. All Randomized Subjects

All screened subjects who were randomized into the clinical study.

9.2.3. Full Analysis Set

All randomized subjects who have received at least 1 dose of IP

9.2.4. Safety Analysis Set

All randomized subjects who have received at least 1 dose of IP.

9.2.5. Pharmacokinetic Analysis Set

Subset of the Safety Analysis Set for which plasma concentration data are available to facilitate development of the population PK model as described in the pharmacometric analysis plan and excluding CSP deviations which have an impact on the PK analyses.

9.2.6. [REDACTED]

[REDACTED]

9.2.7. Pharmacokinetic/ [REDACTED] Analysis Set

Intersection of the PK [REDACTED] Analysis Sets.

9.3. Statistical Analyses

9.3.1. General Statistical Considerations

Summary tabulations will be presented and will display the number of observations, mean, standard deviations (SDs) and/or standard error (as appropriate), median, minimum and maximum (for continuous variables), and the number and percentage per category (for categorical data). In addition to tabulated descriptive statistics, graphical data displays may be used to summarize the data.

Baseline is defined as the last available assessment prior to the first intake of IP. For ECG, the baseline ECG result is the mean of the last available triplicate prior to the first intake of IP.

Unless otherwise noted, inferential statistics will be interpreted at the 2-sided 10% significance level.

9.3.2. Interim Analysis

No formal interim analysis is planned for this clinical study.

9.3.3. Analyses of Demographics and Baseline Characteristics

Subject disposition (including reasons for ED), CSP deviations, demographics, baseline characteristics, medical history, and concomitant therapies will be analyzed descriptively.

9.3.4. Analyses of Efficacy Parameters

Efficacy analysis will be performed on the FAS.

9.3.4.1. Analysis for Primary Efficacy Endpoint

The signal detection methodology described by Frewer et al (21) will be used to provide further insight into the treatment effect of GLPG3970 over placebo, and will support scenario analyses. See also Section 9.1.

A MMRM (ESSDAI) will be used to compare treatment groups, with a 90% confidence interval (CI) of the treatment difference at Week 12.

9.3.4.2. Analyses for Secondary and Other Efficacy Endpoints

Continuous efficacy endpoints, including the primary endpoint: MMRM to compare treatment groups, with a 90% CI of the treatment difference at each time point.

Binary efficacy endpoints: Presented with a 90% exact CI of the treatment difference at each time point.

9.3.5. Analyses of Safety Data

All safety analyses will be performed using the Safety Analysis Set (Section 9.2.4). All safety data collected on or after the first dose of IP administration up to the last contact after the last dose of IP, unless specified otherwise, will be summarized by treatment group according to the IP received. Clinical safety will be addressed by assessing AEs, laboratory assessments, physical examinations, vital signs, and 12-lead ECGs.

9.3.5.1. Extent of Exposure

A subject's extent of exposure to the IP will be generated from the IP administration page of the CRF. Exposure data will be summarized by treatment group. Duration of exposure to the IP will be expressed as the number of days between the first and last dose of IP, inclusive, regardless of temporary interruptions in IP administration and summarized by treatment group.

9.3.5.2. Adverse Events

Clinical and laboratory AEs will be coded using the latest version of the Medical Dictionary for Regulatory Activities. System Organ Class, High-Level Group Term, High-Level Term, Preferred Term, and Lower-Level Term will be attached to the clinical database.

The following AEs will be considered as treatment-emergent adverse events (TEAEs):

Any AE with an onset date on or after the IP start date and no later than 30 days after last dose of IP, or any worsening of any AE on or after the IP start date.

Summaries (number and percentage of subjects) of TEAEs per subject by System Organ Class and Preferred Term will be provided by treatment group. TEAEs will also be summarized by causal relationship to the IP and severity. In addition, TEAEs leading to ED of the IP will be summarized and listed. Also, all SAEs, including the non-treatment-emergent SAEs, will be listed.

9.3.5.3. Clinical Laboratory Evaluations

Laboratory assessments will be analyzed descriptively. Changes from baseline and treatment-emergent shifts according to normal ranges and CTCAE grades will be presented as well. Analyses will be done per treatment group.

9.3.5.4. Physical Examinations

Only abnormal post-baseline physical examination results will be listed, when available.

9.3.5.5. Vital Signs

Vital signs will be analyzed descriptively. Changes from baseline will be presented as well. Analyses will be done per treatment group.

9.3.5.6. 12-Lead Electrocardiogram

A descriptive analysis will be done for the 12-lead ECG. Changes from baseline will be presented as well. Frequency analyses of abnormalities based on actual values and on changes from baseline will be presented as well. Analyses will be done per treatment group.

9.3.6. Pharmacokinetic Analyses

GLPG3970 plasma concentrations will be listed and predose concentrations (C_{trough}) will be summarized descriptively and reported in the CSR.

All observed GLPG3970 plasma concentrations will be analyzed using a population PK approach to characterize the PK profile of GLPG3970. This analysis will provide simulated pop-PK parameters for GLPG3970, such as clearance (CL/F) and V_{ss}, and their associated variability, as well as individual estimates of AUC and, if appropriate, C_{max} . The results from the pop-PK analysis will be reported separately from the CSR.

[REDACTED]

9.3.7. [REDACTED]

[REDACTED]

9.3.8. Analysis of Other Assessments

Not applicable.

9.3.9. Additional Statistical Considerations

Not applicable.

10. DATA MONITORING

10.1. Safety Monitoring Committee

A Safety Monitoring Committee independent from the study will review unblinded data during the course of the study. This Committee will include a physician with experience in drug development, a biostatistician, and a safety physician. External medical experts (such as an expert in the field of pSS and an infectious diseases expert) may be included to support data interpretation. The Committee will review unblinded safety data and assess any potential safety issues arising during the conduct of the clinical study, including (but not limited to) any potential issues in the context of the SARS-CoV-2 pandemic. The process is described in a separate 'Safety Monitoring Committee Charter'.

11. SAFETY REPORTING

11.1. Definitions of Adverse Events, Serious Adverse Events, and Special Situations

11.1.1. Adverse Events

An AE is any untoward medical occurrence, new or worsening of any pre-existing condition, in a clinical study subject administered a medicinal product and which does not necessarily have to have a causal relationship with this treatment.

An AE can therefore be any unfavorable and unintended sign (e.g. an abnormal laboratory finding), symptom, or disease temporally associated with the use of a medicinal product, whether or not considered related. AEs may also include pre- or post-treatment complications that occur as a result of CSP-specified procedures, worsening of the targeted disease, overdose, drug abuse/misuse reports, or occupational exposure. Pre-existing conditions that increase in severity or change in nature during or as a consequence of participation in the clinical study will also be considered AEs.

11.1.2. Serious Adverse Events

An SAE is defined as an AE that:

- Results in death.
- Is life-threatening (Note: The term 'life-threatening' in the definition of 'serious' refers to an event in which the subject was at risk of death at the time of the event; it does not refer to an event that hypothetically might have caused death if it were more severe).
- Requires in-patient hospitalization or prolongation of existing hospitalization.
- Results in persistent or significant disability/incapacity.
- Is a congenital anomaly / birth defect.
- Is medically significant (medical and scientific judgment should be exercised in deciding whether other situations should be considered serious such as important medical events that might not be immediately life-threatening or result in death or hospitalization but might

jeopardize the subject or might require intervention to prevent one of the other outcomes listed in the definition above).

11.1.3. Unlisted (Unexpected) Adverse Events/ Reference Safety Information

An AE is considered unlisted if the nature or intensity is not consistent with the applicable product reference safety information. For an IP, the expectedness of an AE will be determined by whether or not it is listed in the reference safety information part of the IB.

11.1.4. Adverse Events of Special Interest

Not applicable.

11.1.5. Clinical Laboratory Abnormalities and Other Abnormal Assessments as Adverse Events or Serious Adverse Events

Laboratory abnormalities without clinical significance based on the investigator's judgment are not considered AEs or SAEs. However, laboratory abnormalities (e.g. clinical chemistry, hematology, and urinalysis) or other abnormal (clinical study-specific) assessments (e.g. ECG, radiography, vital signs) that require medical or surgical intervention, are associated with signs and/or symptoms, and/or lead to IP interruption, modification or discontinuation must be recorded as an AE or SAE if they meet the definition as described in Sections 11.1.1 and 11.1.2, respectively. If the laboratory abnormality is part of a syndrome, the syndrome or diagnosis is to be reported (e.g. anemia instead of decreased hemoglobin).

The following liver enzyme elevations must be reported as SAEs:

- AST or ALT $\geq 3 \times \text{ULN}$ with signs of liver damage (total bilirubin $> 2 \times \text{ULN}$ OR INR > 1.5 , and/or with the appearance of fatigue, nausea, vomiting, right upper quadrant pain or tenderness, fever, rash and/or eosinophilia [$> 5\%$]).

11.1.6. Special Situations

Special situations are situations that have a possible impact on the safe use of the IP. These situations might be or might not be associated with AEs.

- Pregnancy.

- Overdose with IP.

An overdose of IP is defined as the administration of a quantity of the IP given per administration or cumulatively, which is above the dose of IP given during this study.

- Medication error with IP.

A medication error with IP is defined as an unintended failure in the drug treatment process that leads to, or has the potential to lead to, harm to the subject.

- Product complaint or quality defect of IP.

Product complaint or quality defect of IP is defined as complaints or defects of the IP arising from potential deviations in the manufacture, packaging, or distribution of the IP.

- Abuse or misuse of IP.
Abuse of IP is defined as the persistent or sporadic, intentional excessive use of the IP, which is accompanied by harmful physical or psychological effects.
Misuse of IP is defined as a situation where the IP is intentionally and inappropriately used not in accordance with the product information.
- Drug interaction or food interaction with IP.
A drug interaction with IP is defined as a situation in which there is evidence or a suspicion that the IP interacts with another drug when both are administered together.
A food interaction with IP is defined as a situation in which there is evidence or a suspicion that the IP interacts with a food when taken together.
- Occupational exposure to IP.
Occupational exposure to IP is defined as an exposure to the IP as a result of one's professional or non-professional occupation.

11.2. Assessment of Adverse Events and Serious Adverse Events

The investigator is responsible for assessing AEs and SAEs for causality and severity. This is the basis for the sponsor's final review and confirmation of accuracy and completeness of event information and causality assessments.

11.2.1. Action Taken Regarding Investigational Product (if Applicable)

The action taken must be described by choosing from:

- Dose not changed: In case no action is taken regarding the IP.
- IP permanently discontinued: In case a subject is permanently discontinued from treatment or withdrawn from the study by the investigator (who may consult the sponsor's medical leader).
- IP temporarily discontinued: In case the IP is temporarily discontinued by the investigator (who may consult the sponsor's medical leader).
- Not applicable: Other situations (e.g. in case an AE started after the last IP administration).

11.2.2. Assessment of Causality

The investigator is responsible for assessing the causal relationship to IP(s) administration or study procedures (e.g. invasive procedures such as venipuncture) based on her/his clinical judgment. The following decision choice will be used by the investigator to describe the causality assessment between the reported event or laboratory test abnormality and the IP.

- **Unrelated:**
Time relationship to IP intake is improbable. Related to other etiologies such as concomitant medications or subject's clinical state.
- **Unlikely:**
Time relationship to IP intake is improbable (but not impossible). Concomitant disease or other drugs provide plausible explanations.
- **Possible:**
Time relationship to IP intake is reasonable. Event or laboratory test abnormality could also be explained by disease or other drugs. Information on IP withdrawal may be lacking or unclear.
- **Probable:**
Time relationship to IP intake is reasonable. Unlikely to be attributed to concurrent disease or other drugs. Response to withdrawal is clinically reasonable and rechallenge not required.
- **Certain:**
Time relationship to IP intake is plausible. Cannot be explained by concomitant disease or other drugs. Response to withdrawal is plausible (pharmacologically, pathologically). Event definitive pharmacologically or phenomenologically (i.e. an objective and specific medical disorder or a recognized pharmacological phenomenon). Rechallenge satisfactory, if ethical and necessary.

It should be emphasized that ineffective treatment (worsening of the disease) should not be considered as causally related in the context of AE reporting.

11.2.3. Assessment of Severity

The severity of AEs should be graded using the CTCAE version current at the time of assessment. If a CTCAE criterion does not exist, the investigator should use the grade or adjectives: Grade 1 (mild), Grade 2 (moderate), Grade 3 (severe), Grade 4 (life-threatening), or Grade 5 (fatal) to describe the maximum intensity of the AE. For purposes of consistency with the CTCAE, these intensity grades are defined in [Table 2](#).

Table 2: Grading of AE Severity

Grade	Adjective	Description
Grade 1	Mild	Asymptomatic or mild symptoms; clinical or diagnostic observations only; intervention not indicated
Grade 2	Moderate	Local or noninvasive intervention indicated; limiting age-appropriate instrumental ADL*
Grade 3	Severe	Severe or medically significant but not immediately life-threatening; hospitalization or prolongation of hospitalization indicated; disabling; limiting self-care ADL**
Grade 4	Life-threatening	Urgent intervention indicated
Grade 5	Death	Death-related AE

* Instrumental Activities of Daily Living (ADL) refer to preparing meals, shopping for groceries or clothes, using the telephone, managing money, etc.
** Self-care ADL refer to bathing, dressing and undressing, feeding self, using the toilet, taking medications, and not bedridden.

For AEs associated with laboratory abnormalities, the event should be graded on the basis of the clinical severity in the context of the underlying conditions; this may or may not be in agreement with the grading of the laboratory abnormality. This is upon the investigator's assessment.

If there is a change in intensity (worsening or improvement) of an AE, it must be recorded.

11.2.4. Outcome

Each AE must be rated by choosing among:

- Recovered/resolved;
- Recovered/resolved with sequelae;
- Recovering/resolving;
- Not recovered/not resolved;
- Fatal;
- Unknown.

11.3. Investigator Requirements and Instructions for Reporting Adverse Events, Serious Adverse Events, Pregnancies, and Other Special Situations to the Sponsor

11.3.1. Adverse Events

The AE reporting period for safety surveillance begins when the subject signs the ICF and ends at the subject's last FU visit (the last FU visit after the last dose of IP). In this period, all new AEs,

regardless of cause or relationship, derived by spontaneous, unsolicited reports of subjects, by observation and by routine open questioning (such as “How do you feel?”) need to be recorded in the source and in the CRF.

In case an AE is ongoing at the time of the last FU visit, the investigator needs to follow up on the subject until AE resolution or reasonable stabilization and to document in the subject’s source documentation. No related updates or additional data on the AE should be reported in the CRF.

If a subject is documented as lost-to-FU, ongoing/unknown outcome AEs will not be followed-up.

If the AE meets the criteria for seriousness, the SAE form must be completed and sent to the sponsor within 24 hours (see Section 11.3.2).

11.3.2. Serious Adverse Events

Subjects experiencing an SAE or an emergency situation will be examined by a physician as soon as possible. The subject will remain under observation as long as medically indicated.

Appropriate laboratory tests will be performed until all parameters return to normal or are otherwise explained or stable.

All SAEs, whether or not deemed IP-related, must be recorded on the SAE form and in the CRF. The investigator must report each SAE immediately, and under no circumstances should this exceed 24 hours following the knowledge of the SAE, as is indicated on page 2 under “Emergency Contact Information”.

The SAE form should at least contain identifiers of the subject and the reporter, SAE term and statement of relatedness to the IP, and at a later stage if not yet available within 24 hours, the form needs to be completed with a clearly written narrative describing signs, symptoms, and treatment of the event, diagnostic procedures, as well as any relevant laboratory data and any sequelae.

FU and outcomes should be reported and documented in the source documents for all subjects that experience an SAE. It is important that the information provided on the SAE form matches the information recorded on the CRF for the same event.

Copies of additional laboratory tests, consultation reports, post-mortem reports, hospital case reports, autopsy reports, and other documents should be sent when requested and available. Only subject identifiers (subject number) should appear on the copies, and all names and initials should be blackened and rendered illegible. Follow-up (FU) reports relative to the subject’s subsequent course must be submitted until the event has subsided or, in case of permanent impairment, until the condition stabilizes.

Any SAEs that occur after the post-treatment FU visit but within 30 days of the last dose of IP(s), regardless of causality, should also be reported (Emergency Contact Information on Page 2) but not entered in the CRF. Investigators are not obligated to actively seek SAEs after the CSP-defined FU period. However, if the investigator is informed about an SAE that occurs at any time

after the subjects' post-treatment FU visit and the event is deemed relevant to the use of IP(s), he/she should promptly document and report the event to the sponsor by using the SAE form.

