8.11. Schedule of Activities

For detailed instructions on the clinical study procedures, please see referred sections and Section 8.1, “Timing of Assessments”.

EVENT	SCREENING PERIOD	TREATMENT PERIOD ¹						FOLLOW-UP PERIOD
		1	2	3	4	5	ED ²	
Study Visit	S	1	2	3	4	5	ED ²	Follow-up Visit
Study Week	-4 to -1	Baseline	1	4	8	12		
Study Day (D) ± Days	-28 to -1	1	8±1	29±2	57±2	85±2	Early treatment discontinuation	28 ± 3 after last IP dosing
Informed consent	✓							
Inclusion/exclusion criteria	✓	✓						
Demographics	✓							
Medical history	✓							
Physical examination	✓	✓	✓	✓	✓	✓	✓	✓
Vital signs	✓	✓	✓	✓	✓	✓	✓	✓
Body weight and height ³	✓	✓	✓	✓	✓	✓	✓	✓

¹ On dosing days, all assessments are to be performed predose, unless otherwise specified.

² Subjects who discontinue treatment early will be requested to return for an ED visit and to return for a FU visit 28 ± 3 days after last IP administration.

³ Height only to be measured at screening.

EVENT	SCREENING PERIOD	TREATMENT PERIOD ¹						FOLLOW-UP PERIOD
		1	2	3	4	5	ED ²	
Study Visit	S	1	2	3	4	5	ED ²	Follow-up Visit
Study Week	-4 to -1	Baseline	1	4	8	12		
Study Day (D) ± Days	-28 to -1	1	8±1	29±2	57±2	85±2	Early treatment discontinuation	28 ± 3 after last IP dosing
12-lead ECG ⁴	✓	Predose, 1.5h, 3h, 4.5h postdose ⁴	Predose	Predose	Predose	Predose	✓	✓
QuantiFERON-TB Gold test	✓							
SARS-CoV-2 RT-PCR test ^{5,6}	✓	✓	As needed					
SARS-CoV-2 serology test ^{5,6}		✓	As needed					
Randomization		✓						
Blood collection								
– Safety (hematology, coagulation, chemistry)	✓	✓ ⁷	✓	✓	✓ ⁷	✓ ⁷	✓	✓
– Safety (HBV, HCV, HIV serology)	✓							

⁴ At Visit 1 (Day 1), triplicate ECGs will be recorded predose and at 4.5 hours postdose. At all other timepoints, single ECGs will be taken.

⁵ RT-PCR from a nasal swab sample at screening and RT-PCR from a nasal swab sample and serology testing at Visit 1 (Day 1), and as needed when subject presents signs and symptoms of SARS-CoV-2 infection.

⁶ SARS-CoV-2 RT-PCR and serology tests can (optionally) be sampled by a nurse at the subject's home 2-3 days before Visit 1 (Day 1).

⁷ Fasted glucose, fasted insulin, and HOMA-IR only at Visit 1, 4, and 5.

EVENT	SCREENING PERIOD	TREATMENT PERIOD ¹						FOLLOW-UP PERIOD
		1	2	3	4	5	ED ²	
Study Visit	S							Follow-up Visit
Study Week	-4 to -1	Baseline	1	4	8	12		
Study Day (D) ± Days	-28 to -1	1	8±1	29±2	57±2	85±2	Early treatment discontinuation	28 ± 3 after last IP dosing
– Pregnancy test serum (all females)	✓							

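### Serious adverse events after the follow-up visit but within 30 days of last dose are kept out of the CRF although they meet the TEAE definition, so the serious-TEAE tables and SAE listing may omit them

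*Protocol*

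**What the plan says.** **Collection.** Protocol 11.3.1 runs AE recording in the CRF from consent to the subject's "last FU visit (the last FU visit after the last dose of IP"). The Schedule of Activities (Protocol 8.11) places that visit at "28 ± 3 after last IP dosing".

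**SAE rule.** Protocol 11.3.2 starts with a general requirement: "All SAEs, whether or not deemed IP-related, must be recorded on the SAE form and in the CRF". It then carves out a class of events, "Any SAEs that occur after the post-treatment FU visit but within 30 days of the last dose of IP(s), regardless of causality", which "should also be reported (Emergency Contact Information on Page 2) but not entered in the CRF".

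**Definition.** The TEAE definition in Protocol 9.3.5.2 reads "Any AE with an onset date on or after the IP start date and no later than 30 days after last dose of IP". Worsening of an event once dosing has begun also counts. SAP 6.3.1.1 repeats this. Protocol 9.3.5.2 also commits to listing every SAE, including those that are not treatment-emergent.

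**Analysis.** SAP 6.3.1.8 plans serious-TEAE tables for the CSR, and SAP 6.3.1.9 plans one for EudraCT. SAP 6.3.1 takes all AEs to be in the database. SAP 4.3.2 (Table 2) ends the treatment analysis period at the date of last contact. The safety estimand in SAP Section 3 uses data up to and including the last contact visit. Neither document describes adding SAEs that exist only on the SAE form.

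**The concern.** The definition and the data-entry rule stop at different times. The definition runs to Day 30 after last dose. CRF entry stops at a visit that may take place as early as Day 25 and is nominally on Day 28. An SAE between the two is a serious TEAE by definition, yet site staff are told not to enter it.

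This matters because the number, incidence and severity of TEAEs form one of the two primary endpoints. SAP Section 1 records that the trial was stopped on the Safety Monitoring Committee's recommendation for a liver toxicity signal, and that only the primary endpoint and safety analyses remain. Complete serious-event counts are thus a main product of the abbreviated CSR. Protocol 11.1.5 also makes certain liver enzyme elevations reportable as SAEs, so a late liver event could be among those affected.

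**Working it through.** The plan gives no figure for this gap, so there is nothing to reproduce. The check is a day count, followed by tracing where an affected event would go.

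**Inputs**
- Follow-up visit on day *f* after last dose, with *f* from 28 − 3 = 25 to 28 + 3 = 31 (Protocol 8.11).
- Last TEAE onset day: 30 (Protocol 9.3.5.2, SAP 6.3.1.1).
- Planned arm sizes: 20 on GLPG3970 and 10 on placebo (Protocol 9.1).

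**Step 1: uncovered days.** These are days *f* + 1 to 30, so the count is max(0, 30 − *f*).

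| Follow-up day *f* | Uncovered days | Count | Share of 30-day post-dose window |
|---|---|---|---|
| 25 | 26–30 | 5 | 16.7% |
| 26 | 27–30 | 4 | 13.3% |
| 27 | 28–30 | 3 | 10.0% |
| 28 (nominal) | 29–30 | 2 | 6.7% |
| 29 | 30 | 1 | 3.3% |
| 30 or 31 | none | 0 | 0% |

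The gap therefore does not depend on an early visit; one exactly on schedule leaves two days. For a completer with 85 dosing days, the whole TEAE window is 85 + 30 = 115 days. The gap is then 2/115 = 1.7% at the nominal visit and at most 5/115 = 4.3%.

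**Step 2: where the event goes.** Take an SAE with onset on Day 29 after a Day 28 visit.
1. Protocol 11.3.2: it is reported to the sponsor and not entered in the CRF.
2. Protocol 9.3.5.2 and SAP 6.3.1.1: it is a TEAE, since 29 ≤ 30.
3. SAP 6.3.1.8 and 6.3.1.9: it belongs in the serious-TEAE tables, but no route into the analysis data is described.
4. SAP 6.3.1.3: even if added, it is placed in a period only if its start date is no later than the period end. Under Table 2 that end is the last contact. If last contact was the follow-up visit, the event belongs to no analysis period.

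Step 4 shows why CRF entry alone would not be enough.

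**Step 3: size of one omission.** SAP 6.3.1.8 counts subjects. One missed subject changes the serious-TEAE row by 1/20 = 5 percentage points on GLPG3970 or 1/10 = 10 points on placebo, if that subject had no other serious TEAE. Otherwise that row does not change.

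**The case against.** The strongest reply is that the plan bounds its safety data at last contact: Protocol 9.3.5, SAP Table 2 and the safety estimand all do so, and Protocol 8.5.1 and 11.3.1 end AE collection at the last follow-up visit. On that reading the 30 days are an outer cap on whatever was collected, and 11.3.2 simply follows the collection period. This is a fair account of how the texts may have arisen, but it does not remove the problem. Protocol 11.3.2 expressly foresees these SAEs and requires them to be reported, and 9.3.5.2 promises to list all SAEs. The sponsor would hold events that meet the definition, with no stated place for them in the output.

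Other parts of the reply stand, and they limit what can be claimed:
- A reader might infer that 11.3.2 contradicts itself by requiring CRF entry and then forbidding it. It is better read as a general rule with a specific exception. The mismatch is with the TEAE definition.
- A reader might infer that these events are certain to be missing. Neither document says that the AE tables use CRF data only, and the Data Management Plan (Protocol 12.7.1) is not available here. The text supports only that they may be missing.
- A reader might take 17% as the typical gap, or 5 or 10 points as the cost of every missed event. The first is the extreme visit date set against the post-dose window alone. The second holds only under the condition in Step 3.
- A reader might infer that safety surveillance is weakened. It is not, since these SAEs must be reported to the sponsor regardless of causality. The issue is tabulation, and SAP 6.3 plans no formal testing of safety data.

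**Conclusion.** The concern holds in limited form. Following the protocol as written can leave a serious TEAE out of the CSR and EudraCT tables and out of the SAE listing. The exposure is 0 to 5 days per subject, and 2 days at a Day 28 visit. Few events are expected in so short a time, but arms of 20 and 10 make a single subject visible.

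This rests on three assumptions. The follow-up visit takes place within its permitted window (an earlier visit would widen the gap). No merge of SAE-form data is specified in a document not seen here. Arm sizes are as planned, although the study stopped early and actual numbers may be smaller.

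**What to change.** State in the SAP that:
- SAEs reported on the SAE form with onset up to 30 days after last dose are merged from the safety database into the AE analysis data;
- for these events, the treatment analysis period in Table 2 and the last-contact limit in the safety estimand extend to 30 days after last dose;
- a footnote to the TEAE tables says that non-serious AEs starting after the follow-up visit were not collected.

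With this, the uncovered part of the window for SAEs is 0 days for every permitted visit date. Protocol 9.3.5 allows its last-contact boundary to be specified otherwise, so the SAP is a suitable place. It was also a timely one. If, for illustration, a subject's last dose was on 26 November 2021 (the date of the stopping recommendation), the follow-up visit would fall on 21 to 27 December and Day 30 on 26 December, all after the SAP date of 17 December.

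The cost is a few sentences and a small amount of reconciliation. An amendment for this alone is not warranted, since amendments must go to the ethics committees (Protocol 12.6.1). If the protocol is amended for other reasons, 11.3.2 should be aligned so that these SAEs are entered in the CRF. The remaining downside is uneven capture after the follow-up visit, with SAEs included and non-serious AEs not, which is why the footnote is needed.
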